### **9.2.3 Time to Treatment Failure**

TTF will be analyzed applying a not stratified log rank test. Kaplan-Meier estimates will be presented and Cox regression models be applied as described in Section 9.1.

### **9.2.4 Overall Survival**

OS will be analyzed applying a not stratified log rank test and a proportional hazards regression model including the stratification factors in addition to the study treatment factor. Kaplan-Meier estimates will be presented as described in Section 9.1. Survival rates at 12, 18 and 24 months and associated 95%-confidence intervals will be presented.

A further proportional hazards regression model will be applied including the study treatment factor, the stratification factors and a dichotomous variable for second line treatment. This model maybe further modified or supplemented to account for different classes of second line treatments.

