10.1.5 Follow-Up Phase

Safety Visit (28 + 2 Days After Last Infusion)

Four weeks (28 + 2 days) after the last administration of the study drug, a Safety Visit must be performed for all patients. During this visit, the following assessments will be carried out:

- Physical examination.
- Vital signs (blood pressure, heart rate and body temperature), body weight and BMI.
- 12-lead ECG
- Record ECOG performance status.
- Blood and urine sampling for safety laboratory (hematology, coagulation panel, blood chemistry and urinalysis).
- Blood sampling for assessment of immune status (only in a subset of approximately 30 patients per treatment arm).
- Blood sampling for ADA testing (only for patients receiving CetuGEX™).
- Blood sampling for PK assessments (only for patients receiving CetuGEX™).
- QoL questionnaires EORTC-QLQ-C30 and EORTC-QLQ-H&N35 (to be performed prior to any other assessments).
- Pregnancy test for female patients of childbearing potential.
- Recording of concomitant medication.
- Assessment of AEs.

The Safety Visit is identical to the Final Examination Visit for those patients who received treatment until progression of disease.

Final Examination

As soon as progression of disease is detected, a Final Examination Visit must be performed for all patients who prematurely discontinued study treatment for any other reason except progression of disease.

In case of complete study withdrawal before documented progressive disease, a Final Examination Visit should be performed at the time of premature discontinuation.

The following assessments will be performed:

- Vital signs (blood pressure, heart rate and body temperature).
- Record ECOG performance status.
- Recording of concomitant medication.
- Assessment of AEs.

For patients discontinuing study medication due to progressive disease, the 28-day Safety Visit will constitute the Final Examination.

After the Final Examination, patients will be followed-up by quarterly phone calls until death or for a maximum duration of 24 months after randomization of the last patient for assessment of overall survival. Apart from post-PD anti-tumor therapies, no concomitant medications and no AEs will be recorded after the Final Examination.

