13.4.3.2 Secondary Analyses

A Chi-squared test will be performed to evaluate the effects of treatment on response rates as defined in Section 13.1.2. A logistic regression model will be fit to estimate odds ratios for the association of stratification factors, the p16 status, and the EGFR status with response categories. Corresponding 95%-confidence intervals will be calculated for the treatment differences in response rates.

Overall survival and TTF will be analyzed analogously to PFS on an ITT basis. Additional models will be applied to evaluate the impact of second line treatments on OS. Details will be given in the SAP.

If subgroup sample sizes allow, analyses of the primary and secondary efficacy endpoints will be repeated for the FcγRIIIa-allotype subgroups (i.e., FF, FV, VV), the p16 status subgroups as well as the EGFR status subgroups, omitting the FcγRIIIa factor, the p16 status and the EGFR status factor, respectively.

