### **5. SAMPLE SIZE DETERMINATION**

Approximately 240 patients will be randomized in this study.

The log-rank test will be used to test the hypothesis that patients assigned to the CetuGEX™ arm have increased PFS compared to patients assigned to the control arm.

The sample size calculation is based on the following assumptions:

- The median PFS in the control arm is expected to be 5.6 months post randomization.
- It is expected that the median PFS in the CetuGEX™ arm can be increased to 8.4 months corresponding to a hazard ratio of 0.67.
- The overall trial duration will be approximately 36 months with an anticipated recruitment time of 24 months, anticipated treatment phase until PFS events are reached of approximately 12 months after randomization of the last patient (data

cut-off for main analysis) and ongoing follow-up for overall survival for at least 24 months after randomization of the last patient.

- Drop-outs are expected to occur at times following an exponential distribution and resulting in a drop-out rate of 10% at the cut-off for PFS analysis.
- Patients will be randomized in a 1:1 ratio.
- The overall two-sided significance level will be 0.05 and the power to be maintained 80%.

Based on these assumptions, approximately 240 patients have to be randomized to observe the required overall number of 192 events.

If the required number of events is not reached as planned after 12 months from last patient randomized, the main analysis will be postponed to obtain more events but not more than additional 6 months.

Assuming a corresponding effect on OS (hazard ratio 0.67) and a median overall survival of 10.6 months in the control group the number of survival events to be observed after a 24-months follow-up for survival will be 183.

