### **7.2 Derived and Computed Variables**

The following derived and computed variables have been initially identified as important for the analysis of the primary and secondary target variables. It is expected that additional variables will be required. The SAP will not be amended for additional variables that are not related to the primary target or key secondary target variables. Any additional derived or computed variables will be identified and documented in the SAS programs that create the analysis files. If the SAP is not amended, further derivations required to support the analyses of primary and secondary target variables will be described in the CSR.

Disease will be evaluated by the investigator (modified irRC) and by independent

centralized reading (modified irRC and RECIST 1.1) and classified as complete response (CR), partial response (PR), stable disease (SD) or progressive disease (PD).

Tumor assessments will be performed by the investigator and independent centralized reading during the combination treatment phase and single-agent maintenance phase based on computed tomography (CT) or magnetic resonance imaging (MRI) of the head and neck region, chest, and abdomen. Subsequent assessments will include head, neck and chest; assessments of the abdomen will only be performed if at baseline metastases were confirmed or if clinical evidence suggests new lesions in these regions. Additional regions might be included if clinically indicated.

Tumor assessments in both study arms will be performed at Screening, every 6 weeks after day of randomization until Week 18 and every 8 weeks thereafter. The tumor evaluation will be performed pre-dose. Results of the assessments performed at Screening will be considered baseline values. The same type of imaging as for baseline assessments should be maintained throughout the study.

For time durations in days that need to be converted to months, the number of days will be divided by factor 30.4375. For time durations in days that need to be converted to years, the number of days will be divided by factor 365.25.

The following table describes the derivation of the primary and secondary efficacy variables related to response and survival in detail.

Response Based Variables			
Computation methods described below will be applied simultaneously to response criteria modified irRC (site, central review) and RECIST (central review)			

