Variable Name	Computation Methods, Notes, or Equation(s)		
PFSp  (primary definition)	= Earliest date of progression or death - date of randomization + 1 The earliest date of PD will be used irrespective of PD confirmation		
	Finding	Date of PD of Censoring	Outcome
	No PD or death	Pre and post-baseline imaging done: Date of last imaging	Censored
		No baseline or no post-baseline imaging done: Date of randomization	Censored
	Progression/death documented after a new anticancer treatment has started PD at scheduled visit PD between scheduled visits	Date of last imaging prior to new anticancer treatment Date of imaging Date of imaging	Censored Event Event
PFSs  (sensitivity definition)	= Earliest date of progression or death - date of randomization + 1 The earliest date of PD will be used irrespective of PD confirmation		
	Finding	Date of PD of Censoring	Outcome
	No PD or death	Pre and post-baseline imaging done: Date of last imaging	Censored
		No baseline or no post-baseline imaging done: Date of randomization	Censored
	Progression/death documented after a new anticancer treatment has started PD at scheduled visit PD between scheduled visits*	Date of last imaging prior to new anticancer treatment. Date of imaging Date of next scheduled visit	Censored Event Event
	PD after 2 or more missing scheduled visits	Date of last imaging prior to first missing visit.	Censored
	Death up to 16 weeks (112 days) after last imaging Death later than 16 weeks (112 days) after last imaging	Date of death Date of last imaging	Event Censored
Best overall response	Best modified irRC classification (CR, PR or SD) as assessed by the investigator or by the independent centralized review		

(rates) (BO(R))	SD: follow-up measurements must have met the SD criteria at least once after randomization at a minimum interval of 8 weeks.
Objective response (rate) (OR(R))	Best response of CR or PR
Clinical benefit (rate) (CB(R))	Best response of CR or PR or SD. SD: follow-up measurements must have met the SD criteria at least once after randomization at a minimum interval of 8 weeks

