### 9.1 Primary Efficacy Analysis

The primary efficacy analysis for PFS as assessed by the investigator will be based on the ITT population using the PFSp definition as described in Section 7.2.

A two-sided log-rank test will be used to test the null hypothesis of equal treatment effects at an overall significance level of 0.05. The Kaplan-Meier method will be used to estimate the survival functions. Median survival times together with their 95%-confidence intervals will be retrieved from the survival functions. PFS rates at 6, 12, 15 and 18 months and associated 95%-confidence intervals and graphs of the Kaplan-Meier curves by treatment arm will also be presented.

The primary efficacy analysis will not be stratified by the factors used for stratification at randomization in order to preserve the estimated power considering the high number of strata.

To investigate the influence of the stratification factor on the primary endpoint a Cox regression model will be applied as a sensitivity analysis based on the ITT population. This model will include the treatment effect and the stratification factors

- FcγRIIIa allotypes (FF, FV or VV)
- Oral cavity and oropharynx vs. other locations
- Locally recurrent vs. metastatic disease
- EGFR treatment naïve vs. EGFR treatment as part of multimodal treatment

The hazard ratios, the corresponding 95% confidence intervals and the p-values of the Wald test (using adjustment for ties according to Efron) will be presented for all factors. The Kaplan-Meier analyzes will be repeated separately within the subgroups formed by the stratification factors. Corresponding figures will combine the curves for all treatment group/factor level combinations on one page per factor. Factor levels maybe combined if the sample size per level is  $< 15$ .

Further sensitivity analyses will be done as follows

- The analyses will be repeated using the PFSs definition as described in Section 7.2
- The analyses will be repeated for the PP Population
- It has been recognized that not all sites had strictly applied modified irRC for response assessment. To investigate the influence of deviating response criteria on PFS a log rank test will performed stratifying sites according to strict adherence to modified irRC (yes/no).

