14.2.10.1	ITT, PP	Clinical Benefit Rate (Independent Centralized Reading Based on RECIST 1.1) Frequencies, Chi-Squared Test and Confidence Intervals	16.2.6.2
14.2.10.2	ITT, PP	Clinical Benefit Rate (Independent Centralized Reading Based on RECIST 1.1) Logistic Regression Model	16.2.6.2
14.2.10.3	ITT, PP	Clinical Benefit Rate (Investigator Assessment Based on irRC) in FcγRIIIa-allotype Subgroups - Primary Definition Frequencies and Confidence Intervals	16.2.6.3
14.2.10.4	ITT, PP	Clinical Benefit Rate (Investigator Assessment Based on RECIST 1.1) in Tumor Location Subgroups - Primary Definition Frequencies and Confidence Intervals	16.2.6.3
14.2.10.5	ITT, PP	Clinical Benefit Rate (Investigator Assessment Based on RECIST 1.1) in Recurrence Subgroups - Primary Definition Frequencies and Confidence Intervals	16.2.6.3
14.2.10.6	ITT, PP	Clinical Benefit Rate (Investigator Assessment Based on RECIST 1.1) in EGFR treatment subgroups - Primary Definition Frequencies and Confidence Intervals	16.2.6.3
14.2.11.1	ITT, PP	Duration of Response (Investigator Assessment) Log-Rank Test and Kaplan-Meier Analysis	16.2.6.3
14.2.11.2	ITT, PP	Duration of Response (Independent Centralized Reading based on irRC) Log-Rank Test and Kaplan-Meier Analysis	16.2.6.3

Table Number	Population	Table Title / Summary	Supporting Listing
14.2.11.3	ITT, PP	Duration of Response (Independent Centralized Reading based on RECIST 1.1) Log-Rank Test and Kaplan-Meier Analysis	16.2.6.3
14.2.12.1	ITT, PP	Time to Treatment Failure Log-Rank Test and Kaplan-Meier Analysis	16.2.6.3
14.2.12.2	ITT, PP	Time to Treatment Failure Cox Proportional Hazards Model	16.2.6.3
14.2.13.1	ITT, PP	Overall Survival Log-Rank Test and Kaplan-Meier Analysis	16.2.6.3
14.2.13.2	ITT, PP	Overall Survival Cox Proportional Hazards Model With Stratification Factors	16.2.6.3
14.2.13.3	ITT, PP	Overall Survival in FcγRIIIa-allotype Subgroups Kaplan-Meier Analysis	16.2.6.3
14.2.13.4	ITT, PP	Overall Survival in Tumor Location Subgroups Kaplan-Meier Analysis	16.2.6.3
14.2.13.5	ITT, PP	Overall Survival in Recurrence Subgroups Kaplan-Meier Analysis	16.2.6.3
14.2.13.6	ITT, PP	Overall Survival in EGFR treatment subgroups Kaplan-Meier Analysis	16.2.6.3
14.2.13.7	ITT, PP	Overall Survival – Stratification Factors and Second Line Treatment Cox Proportional Hazards Model	16.2.6.3
14.2.14.1	ITT, PP	Progression Free Survival (Investigator Assessment) – Landmark Analysis Log Rank Test and Kaplan-Meier Analysis	16.2.6.3

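### SAP 9.2.4 sets no timing rule for the second-line-treatment variable in its supplementary OS model; coded ever/never, its hazard ratio can mislead in either direction

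*SAP*

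**What the plan says.** Protocol 13.4.3.2 sets the purpose: "Additional models will be applied to evaluate the impact of second line treatments on OS". It leaves the details to the SAP. SAP 9.2.4 supplies one such model, "including the study treatment factor, the stratification factors and a dichotomous variable for second line treatment". The only extension it mentions is for different classes of second-line treatment, not for timing.

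OS runs from randomization (SAP 7.2). Protocol 9.12.2 bars other anti-cancer treatment until the end of study treatment, so second-line status is always post-baseline. No timing rule appears in the derivation tables of SAP 7.2 or in the title of Table 14.2.13.7 ("Stratification Factors and Second Line Treatment"). The landmark in SAP 9.3.1 is the start of maintenance, which is unrelated to second-line therapy. For variables not listed, SAP 7.2 says: "Any additional derived or computed variables will be identified and documented in the SAS programs that create the analysis files". It adds that, if the SAP is not amended, further derivations for primary and secondary variables will be described in the study report.

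On data capture, Protocol 10.1.5 says: "Apart from post-PD anti-tumor therapies, no concomitant medications and no AEs will be recorded after the Final Examination". SAP 15.2 lists these therapies in Listing 16.2.9.3.

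**The concern.** An ever/never covariate in a model timed from randomization sorts patients by what happens to them later. Two groups are coded as untreated for reasons that have nothing to do with any effect of second-line therapy:

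- Patients who die before they can start it. They make second line look beneficial.
- Patients alive and progression-free at cut-off, who have not needed it. They make second line look harmful.

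The net result depends on the share of PFS events that are deaths, the wait from progression to second line, uptake, prognostic selection, the cut-off and the treatment effect. The documents give planning values only for the last two. At stake is whether the one table meant to answer the protocol's question about second-line therapy can do so.

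**Working it through.** **Inputs from the documents** (SAP 5): 240 patients randomized 1:1; 24 months' accrual; median PFS 5.6 and 8.4 months; OS cut-off 24 months after the last randomization, main-analysis cut-off 12 months after it; 10% drop-out. For OS: "Assuming a corresponding effect on OS (hazard ratio 0.67) and a median overall survival of 10.6 months in the control group".

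**The plan's own figures reproduce.** PFS events by Schoenfeld: 4 × (1.960 + 0.842)² / ln(5.6/8.4)² = 31.4 / 0.1644 = 191, against 192 stated. Deaths at the OS cut-off, exponential OS with 10% observed drop-out: 185, against 183 stated.

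**Model.** The PFS hazard in control is λ = ln 2/5.6 = 0.1238 per month. A share f of PFS events are deaths. The post-progression hazard μ is set so that control median OS is 10.6 months:

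S(t) = e^(−λt) + (1 − f) λ (e^(−μt) − e^(−λt)) / (λ − μ)

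For f = 10%, μ = 0.188: 0.2693 + 0.1114 × (0.1363 − 0.2693)/(0.1238 − 0.188) = 0.2693 + 0.2307 = 0.50. Post-progression medians are 3.3 to 5.1 months across the settings.

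**Size of the progression-free group at cut-off.** With uniform accrual and no drop-out the share is e^(−λF)(1 − e^(−24λ))/(24λ), where F is months after the last randomization.

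- Control: 0.0513 × 0.9487/2.971 = 1.6% at F = 24; 0.2264 × 0.9487/2.971 = 7.2% at F = 12.
- CetuGEX (λ = 0.0825): 0.1380 × 0.8620/1.980 = 6.0% at F = 24; 0.3715 × 0.8620/1.980 = 16.2% at F = 12.

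The upward pull is therefore stronger at the earlier cut-off and under the planned effect.

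**Ever/never hazard ratio, true second-line effect nil.** Assumed, not in the documents: 62% uptake unrelated to prognosis; exponential waits; death shares and median waits as listed. Planned effect: PFS HR 0.667, with the post-progression hazard ratio (0.84 to 0.91) set so that OS HR is 0.67. Each cell gives the 24-month / 12-month cut-off, 400,000 simulated patients per setting; repeat runs agreed within about 0.02.

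| Deaths as share of PFS events, median wait | No treatment effect | Planned effect |
|---|---|---|
| 10%, 1 month | 0.83 / 0.95 | 0.93 / 1.09 |
| 15%, 1.5 months | 0.76 / 0.85 | 0.85 / 0.97 |
| 20%, 1 month | 0.76 / 0.84 | 0.83 / 0.95 |
| 30%, 2 months | 0.64 / 0.68 | 0.69 / 0.76 |
| 10%, none | 1.00 / 1.19 | 1.11 / 1.37 |
| 0%, none | 1.14 / 1.41 | 1.28 / 1.63 |

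In trials of 240 (nominal 2.5% per direction), false benefit reached 91% (30%, 2 months, no treatment effect, 24 months). False harm reached 91% (0%, no wait, planned effect, 12 months). In the 10%, no-wait setting with no treatment effect at 24 months, false harm was 3%.

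**Uptake matters.** For 15%, 1.5 months, no treatment effect, 24 months: 0.80 at 40% uptake and 0.67 at 90%. A wider grid (deaths 5 to 35%, uptake 40 to 90%, delay 0 to 2 months, 3,000 patients per setting) gave 0.52 to 1.64 at 24 months and 0.63 to 2.29 at 12 months.

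**Treatment hazard ratio in the ever/never model**, adjusted against unadjusted:

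- Equal 62% uptake (15%, 1.5 months, planned effect, 24 months): 0.67 against 0.67.
- Equal 90% uptake, no wait, planned effect, 12 months: 0.70 against 0.67 (10% deaths) and 0.71 against 0.65 (0% deaths), that is 0.03 and 0.06 apart.
- Uptake 80% control, 40% CetuGEX (15%, 1.5 months, 24 months): 0.63 against 0.68 under the planned effect, 0.92 against 1.00 with no effect. Reversed: 0.70 against 0.68, and 1.09 against 1.00.

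**Alternative codings, true second-line effect nil.**

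- Time-dependent second line alone: about 1.9 to 5 at 62% uptake, more at higher uptake, because it stands in for progression.
- Time-dependent second line plus time-dependent progression: 0.98 to 1.02. This is a best case, since the simulated structure matches the model. It becomes 1.04 to 1.06 if progression is recorded 6 weeks late in 30% of patients.

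**The case against.** The strongest case against has four parts.

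- **The SAP does not say ever/never.** A dichotomous variable can be a time-dependent 0/1 variable, and SAP 7.2 lets derivations be settled in the programs or described in the report. This stands in part: the gap can be closed without contradicting the SAP. But those routes disclose a coding; they do not fix one in advance.
- **The bias is not certain.** A reader might infer that immortal time always flatters second-line therapy, or that the coefficient must be wrong. The documents support neither. Some settings give about 1.0, and others give false harm.
- **The reach is small.** A reader might also infer that the OS comparison is compromised. It is not: this is one further model with no alpha and no decision rule attached.
- **The remedy is imperfect.** This stands. With fitter patients selected for second line (post-progression hazard ratio 2 between prognostic groups, uptake 80% against 50%), the time-dependent model gives about 0.79 to 0.84 when the truth is 1. It is not always nearer the truth than ever/never: 0.79 against 0.99 with 10% deaths and no wait at 24 months. It is clearly better with 30% deaths and a 2-month wait (0.82 against 0.61). Other selection patterns gave 0.61 to 1.31.

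**Conclusion.** The point holds as a minor-to-moderate one. SAP 9.2.4 leaves the timing of the second-line variable undefined. On its plain reading, the hazard ratio in Table 14.2.13.7 can fall clearly below or above 1 when second-line therapy does nothing: about 0.63 to 1.4 at 62% uptake with no treatment effect, and wider otherwise. In one setting (10% deaths, 1-month wait, planned effect) it moves from 1.09 to 0.93 between the two cut-offs through follow-up alone.

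The figures show range and sign; they do not predict this trial's result. Uptake, wait, death share and selection are all assumptions, and the randomization stratification factors were not simulated. The adjusted treatment hazard ratio is usually close to the unadjusted one. It can differ by about 0.03 to 0.06 even with equal uptake, and by up to 0.09 in the unequal-uptake examples. Primary PFS, the OS log-rank test and the main OS Cox model are unaffected.

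**What to change.** In SAP 9.2.4:

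- Code second-line therapy as time-dependent (0 before its start date, 1 from then on), together with time-dependent progression status. Do not enter second line alone.
- State which assessment supplies the progression date. This matters because SAP 9.1 notes: "It has been recognized that not all sites had strictly applied modified irRC for response assessment".
- State how progression is coded for patients who start new therapy before documented progression. SAP 7.2 censors their PFS ("Date of last imaging prior to new anticancer treatment") but gives no rule for this model.
- Confirm that start dates are captured for therapy first given after progression. The protocol provides for recording such therapies but mentions no start date for them.
- Label the coefficient descriptive, and state that selection of fitter patients still confounds it.
- State that the OS treatment effect is read from the log-rank test and the Cox model without these post-randomization terms. Conditioning on progression removes the effect that acts through PFS: under the planned effect, the treatment hazard ratio in this model is about 0.80 to 0.87, against an OS hazard ratio of about 0.66.

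The cost is some SAP wording, a counting-process data set for one table and a check of the case report form. The change removes the timing bias only; confounding by prognosis and a small bias from late progression dates remain.
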